3.3.3 Supportive/ additional Endpoint

- Time to Hemostasis from patient randomization (TTHR).

3.4 Sample Size Calculation

A sample size of 15 patients per arm was considered as sufficient for the planned descriptive analyses and 95% confidence intervals of efficacy. Dropped patients during the course of the study will be replaced.

3.5 Randomization

A master randomization has been prepared for an excess of patients respect to sample size (patients has been randomized) using the software R.

Considering that in the study are involved three (3) centers in a competitive enrolment, a dynamically assignment of one or more blocks per time at each centre will be performed.

	STATISTICAL ANALYSIS PLAN	FSTAT.01.03
Study Code: HEM-HEM-01-17	Sealantium Medical Ltd.	

4 STATISTICAL ANALYSIS SETS

4.1 Definition of Sets for Statistical Analysis

Safety Analysis Set (SAF)
The Safety Analysis Set will consist of all patients who received at least one dose of any study medication.
Full-Analysis Set (FAS1)
FAS is defined as all randomized patients who underwent surgery, received at least one dose of study treatment and having no major violations of inclusion and exclusion criteria. Patients will be analyzed according to the treatment randomized regardless of which treatment was actually received.
Full-Analysis Set (FAS2)
FAS2 is an extension of the FAS1 and is defined as all randomized patients who underwent surgery, received at least one dose of study treatment.
Per-protocol set (PPS)
All patients according to the FAS definition without important/ major protocol deviations as specified in sec. 4.2.

For application of the different analysis sets to the analyses to be performed see sec. 6.3.

4.2 Violations and Deviations

Protocol violations or deviations (PD) are any non-adherences to the procedures outlined in the study protocol and its referenced manuals and include, but are not limited to, late evidence of exclusion criteria, missed evaluations, incorrect timing of evaluations or dosing and intake of prohibited medication.

Important/ major protocol deviations or violations (IPD) are a subset of protocol deviations that may significantly impact the completeness, accuracy, and/or reliability of the study data or that may significantly affect a subject's rights, safety, or well-being. The study team (contract research associate (CRA) and project manager (PM)) in collaboration with the Sponsor will classify every PD as minor or major according to the classification provided in Monitoring Plan. The final Protocol Deviation Tracking Log will be available in the study archive. Additional PDs emerging from the edit checks and data cleaning process will be processed and evaluated in the same way.

During training and study monitoring, the Investigators and center personnel will be informed that no deviations from, or changes of, the protocol should be initiated without prior written IRB/IEC approval/favorable opinion of an appropriate amendment, except when necessary to eliminate immediate hazards to the subjects or when the change(s)

	STATISTICAL ANALYSIS PLAN	FSTAT.01.03
Study Code: HEM-HEM-01-17		Sealantium Medical Ltd.

involves only logistical or administrative aspects of the trial (e.g., change of monitor(s), telephone number(s)).

Protocol Deviations will be classified (PD/IPD) by PM and Sponsor (in collaboration) and tracked in a Protocol Deviation Register.

Prior to the statistical analysis, all protocol deviations will be listed and assessed as major (or serious) or minor during a blind data review meeting (BDRM) prior to database lock. Each deviation will be discussed case by case with the Sponsor. A major violation may also be a combination of minor deviations.

5 DATA REVIEW

5.1 Data Handling and Transfer

The data from this study will be verified and cleaned by the Data Management group at CRO in accordance with the study handling manual and data clarification policies. The data will be provided to the statistician as SAS datasets. The preferred term and system organ classification (SOC) from the version of MedDRA dictionary used will be provided for all Adverse Events collected. The ATC (Anatomical Therapeutic Chemical) group and sub-group from the relevant version of the WHO-DRUG dictionary will be provided for all prior and concomitant medications.

5.2 Data Review Meeting

When the database will be considered clean by data management, a set of blinded listing will be produced and distributed to the study team for the final review. A meeting will be held to review any data values requiring investigation or correction and to confirm the doubt protocol deviations reported during the study monitoring. The target of this revision is to consolidate the population used for all analyses.

After data review meeting will be also decided exploratory analyses on sub-groups (single patch and more patches) because these analyses are conditioned, even though are only descriptive, by the size of sub-groups.

All actions and changes defined during data review meeting will be consolidated in a written report supporting any implementations or changes in the analyses as defined in the protocol.

Once all data issue has been resolved, study database will be locked and data listing will be produced.

6 STATISTICAL ANALYSIS METHOD

6.1 General Principles

In general, categorical data will be presented using counts and percentages, whilst

	STATISTICAL ANALYSIS PLAN	FSTAT.01.03
Study Code: HEM-HEM-01-17		Sealantium Medical Ltd.

continuous variables will be presented using the mean, standard deviation, standard error of mean, median, minimum, maximum and number of patients. Minima and maxima will usually be reported to the same level of accuracy as the raw data; means, medians, will be presented to one further decimal place; standard deviations and standard errors will be presented to 2 decimal places more than the raw data. Percentages will be rounded to the nearest integer or with one decimal. In tabulations, denominators for calculation of percentages will be taken as the number of non-missing responses in the specified analysis population and treatment group unless otherwise stated. 95% Clopper-Pearson Confidence Intervals for the means or the percentages will be produced if appropriate to explain the results [1].

Table will display data for each treatment group and overall (=Total column).

All data recorded in the CRF will be listed and sorted by treatment groups, subject number and visits [See Appendix 1].

Considering that the study is designed as phase I/II, in which phase I concerns to the primary endpoint (Safety) and phase II concerns to the preliminary data on effectiveness of sFilm-FS, data will not be presented in the two distinct frames, phase I and phase II.

The probability level for all analyses will be set at 5% and appropriate 95% Confidence Intervals will be produced according to the nature of the variables and will be based on a valid case approach, if so [e.g. percentages will be based on the number of observations available at the specific time point and not based on the number of patients at the visit.

6.2 Software used for Statistical Analysis

Statistical calculations will be performed using the statistical package SAS® (Statistical Analysis System) version 9.4.

6.3 Study Population considered in the Statistical Analysis

The primary endpoint of the study and all safety endpoints will use the Safety Set SAF while efficacy endpoints will use the Full-Analysis Sets FAS1, FAS2 and PPS. As Disposition and baseline characteristics will be displayed for all patients (disposition table), SAF, FAS and PPS for further tables on baseline characteristics. Analyses populations will be determined in a (blinded) data review meeting.

6.4 Subpopulations considered in the Statistical Analysis

A stratified analyses using patients with one patch and patients using more patches may be done following recommendations from the BDRM.

6.5 Handling of Missing Values

In accordance with the Study Protocol, no substitution or specific approach for missing data will be applied.

	STATISTICAL ANALYSIS PLAN	FSTAT.01.03
Study Code: HEM-HEM-01-17		Sealantium Medical Ltd.

6.6 Multiple Comparison/ Multiplicity

No correction for multiplicity will be implemented due to the explorative nature of the study. All results must be seen as fully explorative.

6.7 Multicentre Studies

Subgroup analyses or adjustments by center are not reasonable because of too few patients per site.

6.8 Baseline Values

Baseline values are the ones measured short before application of the Investigational medicinal product (IMP).

6.9 Patients Disposition

The number and percentage of patients screened, randomized and treated in the study will be presented, together with the patients who withdrew from the study prematurely prior to Month 6 (Visit 9). Number and percentage of patients included in each of the analysis populations will also be tabulated.

Table will also display this information for each center.

Reasons for early withdrawal will be tabulated with counts and percentages.

Data on informed consent and randomization, analysis set assignments as well as patients with major or minor protocol deviations will be listed. All data relating to study completion or withdrawal will also be listed.

6.10 Demographic and Baseline Characteristics

Summaries of screening data will be produced using SAF, FAS and PPS populations and will be presented by treatment groups and overall.

Data for parameters measured at screening that are also measured at subsequent time points (e.g. physical examination, concomitant medications, clinical-chemical tests) will not be presented in this section. All screening and baseline data will be listed.

6.10.1 Demographic data

Summary statistics for age (years), height (cm), weight (kg) and BMI (kg/m²) at screening will be presented, together with frequency counts and percentages for race and gender.

6.10.2 Significant Medical History

The total number and percentage of patients reporting any significant medical history and the total number and percentage of patients reporting significant occurrences ongoing at screening will be presented. In addition as medical history will be coded along MedDRA version 25.1, the number of medical histories, number and percentage of patients

	STATISTICAL ANALYSIS PLAN	FSTAT.01.03
Study Code: HEM-HEM-01-17	Sealantium Medical Ltd.	

reporting an item of significant medical history will also be presented by System Organ Class (SOC) and Preferred term (PT).

6.11 Surgery, Hepatic Parenchyma Characteristics and Target Bleeding Site (TBS)

Summary of surgery technique and timing, as reported in the eCRF, will be listed and summarized by treatment group. Surgery duration (minutes), time of stay in operating room (minutes), time from liver resection/ incision to fascial closure (minutes), drain usage, estimated blood loss, whether patient is transfused or not, number and blood volume of transfusions used (mL) during surgery, cell salvage used, type of cell salvage, time in Intensive Care Unit (ICU) (hours) and overall length of ICU stay (days) will be presented with the appropriate descriptive statistics.

Concerning Hepatic Parenchyma, summary of data related to the clinical characteristics (hepatic parenchyma classification type) will be tabulated by treatment group.

Data related to TBS (description of TBS via area, density, type and intensity of flow, estimated and total resected TBS treated area (cm²), number of product units applied at the TBS and at other areas, post-operative bile leaks requiring intervention (and if yes how many leaks), hepatic segment) will be presented with the appropriate descriptive statistics and 95% confidence limits of the treatment difference will be calculated where appropriate.

6.12 Safety Evaluation

As previously stated, Safety is the primary endpoint.

Safety could be a composite endpoint because include more than one variable:

- ✓ Adverse Events
- ✓ Thrombotic Events
- ✓ Transfusion-Related Complications
- ✓ MRI Assessment (post-operative adhesions)
- ✓ Signs of Systemic Inflammations
- ✓ Antibodies against Fibrinogen and Thrombin
- ✓ Physical Examination
- ✓ Vital Signs
- ✓ Blood and Coagulation Parameters
- ✓ Urine Analyses

All Safety data will be listed by patients and treatment groups at each collected time and tabulated with the appropriate descriptive statistics by treatment groups at each collected

	STATISTICAL ANALYSIS PLAN	FSTAT.01.03
Study Code: HEM-HEM-01-17		Sealantium Medical Ltd.

time.

Considering that no hypothesis testing for difference between treatments groups concerning AEs related to bleeding at TBS and the other safety data was planned in the protocol, only 95% confidence limits on differences between treatments will be done.

Concerning safety data, an independent data review will be done by a medical reviewer before data review meeting and database lock. The medical reviewer will identify and classify all safety endpoints with respect to e.g. thrombotic events, transfusion complications, etc. and will check correctness of MeDDRA classification (PT, SOC). At the end of this review, medical reviewer will be produced a detailed report.

6.12.1 Transfusion requirements and transfusion related complications for patients transfused

Concerning transfusions, summary statistics for the number of patients received transfusion at each visit. The number of patients who received transfusions will be used as denominator for percentages calculations. Total number of transfusions and total number of units transfused over the whole study period (as a sum from surgery until EoS) will be produced by treatment. Reasons for transfusions (based on number of transfusion) will be presented by counts and percentages.

Number and percentage of patients with transfusion related complications will be summarized by treatment. Number and percentage of related complications by SOC and PT following the layout of adverse event tables (cf. next section) will be produced, too. Related complications are depicted from the adverse event page.

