3.3 Study Endpoints

3.3.1 Primary Endpoint

The primary endpoint of the study consists of multiple safety variables as a composite marker for the safety. Variables of the composite marker were assessed during all study periods: from randomization to end of follow-up. It includes evaluation of treatment emergent adverse events (TEAEs), particularly TEAEs related to bleeding at TBS, thrombotic events, transfusion-related complications, post-operative adhesions (MRI assessment). It also includes evaluation of vital signs, physical examination, urine analysis, blood/coagulation parameters profiles, antibodies against fibrinogen and thrombin, and signs of systemic inflammation.

Primary endpoint is considered as a composite endpoint, because it includes multiple explanatory variables that support safety and tolerability of study treatment on the efficacy claim.

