6.13.7 Incidence of Transfusion Requirements

The number of patients requiring transfusion during the 6 months follow up period will be determined.

Data will be presented only with the appropriate descriptive statistics and exact 95% Clopper-Pearson confidence interval of the difference between treatments.

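### SAP 6.12.1 divides by-visit transfusion counts by the number of transfused patients, so the percentages are not risks per treated patient; the denominator for transfusion complications is left unstated

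*SAP*

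**What the plan says.** SAP 6.12.1 is headed "Transfusion requirements and transfusion related complications for patients transfused". Its first paragraph plans the number of patients transfused at each visit and then fixes the base: "The number of patients who received transfusions will be used as denominator for percentages calculations". It does not say whether that means ever transfused or transfused at the visit being tabulated.

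The second paragraph of 6.12.1 turns to complications: "Number and percentage of patients with transfusion related complications will be summarized by treatment". It names no denominator. The SOC and PT tables for complications are to be produced "following the layout of adverse event tables".

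Three other places bear on this:

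- SAP 6.1 sets the default base as non-missing responses "in the specified analysis population and treatment group unless otherwise stated". The sentence in 6.12.1 is such an exception.
- SAP 6.3 assigns the primary endpoint and all safety endpoints to the SAF.
- SAP 3.3.1 lists "transfusion-related complications" within the primary endpoint. Transfusion requirement is not in that list; it is a secondary endpoint (SAP 3.3.2, Protocol 12.2).

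Two other sections also report transfusion. SAP 6.11 summarises by arm whether the patient was transfused during surgery. SAP 6.13.7 gives the six-month figure: "The number of patients requiring transfusion during the 6 months follow up period will be determined".

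**The concern.** Randomisation makes the two arms comparable as whole arms. The subset that goes on to be transfused is selected after the patch has been applied, and fewer transfusions is one of the effects a better haemostat might have. Dividing by that subset gives up the randomised comparison in the table where a reader will look for it.

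The stakes are moderate. The by-visit figures concern a secondary endpoint. If the same base carries over to complications, a component of the primary safety endpoint would also be shown as a share of a selected subset. SAP 6.12 plans 95% confidence limits on treatment differences for safety data, so an unsuitable base could pass into those differences too.

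**Working it through.** **Inputs**

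- Patients per arm: 15 (SAP 3.4). I assume 15 per arm in the SAF; replacement of dropouts could raise this.
- Denominator: patients who received transfusions (SAP 6.12.1).
- Transfusion and complication rates: not given in the documents. I assume 20–60% transfused and 10–40% with a complication among those transfused. All counts below are illustrations.

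**The plan's own figure.** The documents state no precision figure for transfusions. The one they do give is in Protocol 14.8.2: 80% of 15 patients, exact 95% CI 52% to 96%. Clopper-Pearson for 12/15 has lower limit Beta(0.025; 12, 4) = 51.9% and upper limit Beta(0.975; 13, 3) = 95.7%, so it reproduces. The intervals below use the same method.

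**Possible readings of the by-visit percentage.** Let x be the number transfused at a visit, T the number ever transfused and n the number treated in the arm.

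| Base | Formula | What it shows |
|---|---|---|
| Ever transfused | x/T | when transfusions happened, not how often |
| Transfused at that visit | x/x | 100% by construction |
| Either, with nobody transfused | 0/0 | undefined |
| All treated | x/n | risk per treated patient |

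If each arm had a 20% transfusion rate, the chance that at least one arm had nobody transfused would be 1 − (1 − 0.8^15)² = 6.9%.

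**When the direction reverses.** With equal n, A has the higher risk if xA/xB > 1. The ever-transfused base compares xA/TA with xB/TB. The order is therefore reversed when 1 < xA/xB < TA/TB. The same holds for complications, with x as the number of patients with a complication.

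**A later visit.** Assume A has 10 ever transfused, 4 of them at this visit, and B has 2 ever transfused, 1 at this visit. Then xA/xB = 4 and TA/TB = 5.

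- Per treated patient: 4/15 = 26.7% v 1/15 = 6.7%; A is higher.
- On the ever-transfused base: 4/10 = 40% v 1/2 = 50%; B is higher.

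**At surgery.** Assume A has 2 ever transfused, both at surgery, and B has 6, of whom 3 at surgery. SAP 6.11, on the default base, would print 2/15 = 13% v 3/15 = 20%. SAP 6.12.1 on the ever-transfused base would print 2/2 = 100% v 3/6 = 50% for the same transfusions. The distortion can run against either arm.

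**Complications, if the same base applies.** Assume A has 9 transfused and 2 with a complication, and B has 2 transfused and 1 with a complication.

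- Per treated patient: 2/15 = 13.3% (95% CI 1.7–40.5) v 1/15 = 6.7% (0.2–31.9).
- Per transfused patient: 2/9 = 22.2% (2.8–60.0) v 1/2 = 50.0% (1.3–98.7).

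**How often this would happen for complications.** Exact binomial probabilities of reversal, given unequal complication counts and at least one transfused patient per arm:

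| Transfused, A v B | Complications among transfused, A v B | Probability of reversal |
|---|---|---|
| 20% v 20% | 10% v 10% | 0.6% |
| 30% v 30% | 20% v 20% | 3.1% |
| 40% v 20% | 20% v 20% | 7.4% |
| 60% v 20% | 20% v 20% | 16.7% |
| 60% v 20% | 20% v 40% | 27.0% |

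Reversal is rare when the arms are transfused about equally often, and much more frequent when they are not.

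**The case against.** The strongest reply is that the arm-level comparison is not lost. SAP 6.11 gives surgical transfusion by arm on the default base, SAP 6.13.7 gives six-month transfusion with a between-arm interval, and Protocol 14.8.2 requires the proportion with transfusion requirements by arm. Safety data are also listed by patient and counts accompany percentages, so with about 15 per arm a reader can rebuild the rates. The study is descriptive, with no tests. A share among transfused patients is also a legitimate supplementary display. All of this stands and limits the importance of the point. It does not cover the later visits or the complications: 6.11 stops at surgery, and 6.13.7 is a single overall figure which, as an efficacy endpoint, uses FAS1, FAS2 and PPS under SAP 6.3.

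A reader might infer that the SAP explicitly divides a primary-endpoint component by transfused patients. It does not. The denominator sentence sits in the paragraph on transfusions by visit, the complications paragraph is silent, and the adverse-event layout could equally imply the SAF. The mock tables that might settle it are in a separate document (SAP Appendix 2). For complications the defect is an ambiguity.

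A reader might also infer that an arm with fewer transfusions must show larger percentages. That is not general, because the numerator falls too. With the same complication risk per transfused patient, the expected share is unchanged.

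**Conclusion.** The point holds for the by-visit transfusion percentages in SAP 6.12.1. The base is explicit, it is a post-randomisation subset, and under neither reading is the result a risk per treated patient. For transfusion-related complications the same base is suggested by the heading but not written, and it needs to be settled because they belong to the primary safety endpoint.

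How far the tables would mislead depends on the transfusion counts, which the documents do not anticipate. Under the assumed rates, reversal for complications ranges from 0.6% with similar transfusion rates to 27.0% with a wide gap. Even without reversal, the ever-transfused base multiplies each arm's rate per treated patient by n/T, a factor that differs between arms when their transfusion rates differ. The point is worth correcting before database lock, but it does not threaten the study's conclusions as a whole.

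The totals in 6.12.1 are taken "as a sum from surgery until EoS", and patients are randomised during surgery. A reader might infer that only transfusions after product application should count. The documents do not support that step here: it would redefine a secondary endpoint, and they do not show that transfusion times relative to application are collected.

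**What to change.** In SAP 6.12.1, replace the denominator sentence. Use all SAF patients in the arm as the base for the by-visit transfusion percentages and for patients with transfusion-related complications. At later visits use SAF patients still in follow-up, which fits the valid-case rule in SAP 6.1. Apply the same base to the SOC and PT tables of complications.

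Keep the share among transfused patients only as a labelled supplementary column. State whether it means ever transfused or transfused at that visit, and print it as not estimable when an arm has no transfused patient.

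The cost is a change of SAP wording and one table shell, with no new data. The percentages will be smaller than under the present rule. SAP section 2 says the plan is finalised after the data review meeting and before lock, so there is a natural place to make the change.
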